## Synopsis

**Title:**

A Randomized, Double-Blind, Placebo-Controlled, Multicenter, Parallel-Group Study to Evaluate the Efficacy and Safety of ETX-018810 in Subjects with Diabetic Peripheral Neuropathic Pain

**Short Title:**

Efficacy and Safety of ETX-018810 for the Treatment of Diabetic Peripheral Neuropathic Pain

**Rationale:**

ETX-018810 is a new chemical entity that is under development as a non-opioid treatment for chronic pain syndromes. ETX-018810 is a prodrug of palmitoylethanolamide (PEA), an endogenous bioactive lipid that has shown efficacy in a broad range of nonclinical inflammatory and neuropathic pain models and in clinical trials in chronic pain indications, including diabetic peripheral neuropathic pain (DPNP). [REDACTED]

[REDACTED] The existing published clinical validation of the efficacy of PEA and the safety and tolerability of ETX-018810 in nonclinical studies and in a Phase 1 single- and multiple-, ascending-dose study support its potential as a treatment for DPNP, a pain condition for which there is a high unmet medical need due to the suboptimal efficacy and unacceptable adverse effects of current therapies. This study is designed to evaluate the efficacy, safety, and tolerability of ETX-018810 for the treatment of DPNP.

**Objectives and Endpoints:**

The study objectives and endpoints are summarized in [Table S-1](#).

**Table S-1: Study Objectives and Endpoints**

Objectives	Endpoints
Primary	

 
To evaluate the efficacy of ETX-018810 on neuropathic pain via daily pain measurements in subjects with diabetic peripheral neuropathic pain (DPNP)
 
	
 
Change from baseline to Week 4 in the weekly average of the daily pain score as derived from the subject's responses on the Pain Intensity Numerical Rating Scale (PI-NRS)
 

Secondary	

 
To evaluate the efficacy of ETX-018810 on additional measures of pain and disability
 
	
 
Response rate, defined as a <math>\geq 50\%</math> reduction from baseline to Weeks 1, 2, 3, and 4 in the weekly average of the daily pain score
 
Response rate, defined as a <math>\geq 30\%</math> reduction from baseline to Weeks 1, 2, 3, and 4 in the weekly average of the daily pain score
 
Change in the weekly average of the daily pain score from baseline to Weeks 1, 2, and 3
 
Response rate on the Clinical Global Impression of Change (CGIC) scale at Week 4, defined as the proportion of subjects who are “much improved” or “very much improved”
 
Response rate on the Patient Global Impression of Change (PGIC) scale at Week 4, defined as the proportion of subjects who are “much improved” or “very much improved”
 
Change in the weekly average of the daily sleep score on the Daily Sleep Interference Scale (DSIS) from baseline to Weeks 1, 2, 3, and 4
 
Change in the Brief Pain Inventory (BPI) – Interference Scale from baseline to Week 4
 
Change in the BPI-Pain Scale from baseline to Week 4
 
Amount and pattern of acetaminophen use
 

 
To investigate the safety and tolerability of ETX-018810 in subjects with DPNP
 
	
 
Nature, frequency, and severity of nonserious and serious treatment-emergent adverse events (TEAEs)
 
Frequency of discontinuations due to TEAEs or death
 
Nature, frequency, and severity of posttreatment adverse events (AEs)/serious adverse events (SAEs)
 

**Table S-1: Study Objectives and Endpoints (Continued)**

Objectives	Endpoints

 
To characterize the pharmacokinetics (PK) of ETX-018810 in subjects with DPNP
 
	
 
Plasma concentrations and plasma PK parameters (maximum observed drug concentration [<math>C_{max}</math>] over the first 5 hours after dosing and area under the plasma concentration-time curve computed up to 5 hours after dosing [<math>AUC_{0-5h}</math>]) of palmitoylethanolamide (PEA)
 

1. Participation in the PK component of the study is optional.
2. Subjects will record their PI-NRS score over the last 24 hours once daily in the evening and their DSIS score once daily in the morning in the electronic diary (eDiary) from screening until the baseline/Day 1 visit. The values that are recorded for the PI-NRS and DSIS on the last 7 days before the baseline/Day 1 visit will be used to determine the baseline scores.
3. Subjects will record their PI-NRS score over the last 24 hours in the eDiary, once daily in the evening (when they take their second daily dose of investigational product).
4. Subjects will record their DSIS score in the eDiary once daily in the morning (when they take their first daily dose of investigational product).
5. Subjects will record rescue medication (acetaminophen) use in the eDiary once daily in the evening (when they take their second daily dose of investigational product).

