Subjects will be contacted by telephone to review their status at the end of Week 2 and will report to the clinic for an end-of-treatment (EOT) visit at the end of Week 4. A final posttreatment follow-up telephone contact will be made 1 week after the last dose of investigational product (Week 5) to inquire about adverse events (AEs) and concomitant medication use. Subjects who discontinue from the study before completing the planned 4 weeks of treatment will undergo an early termination visit, which will include the evaluations that are scheduled for the Week 4 visit. If an ongoing automated review of the eDiary reveals that the subject is not complying with study procedures, site personnel will contact the subject to discuss any issues in an effort to improve compliance.

Subjects will take their first dose of investigational product in the clinic on Day 1 (baseline),  

Blood specimens for plasma concentrations of PEA and for calculation of plasma pharmacokinetic (PK) parameters of PEA will be obtained before 

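### Does the PK endpoint need a stated correction for endogenous PEA before Cmax and AUC0-5h can be used?

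*Combined protocol and SAP*

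**What the plan says.** Table S-1 (Continued) in the Synopsis sets a secondary objective: "To characterize the pharmacokinetics (PK) of ETX-018810 in subjects with DPNP". The endpoint for it begins "Plasma concentrations and plasma PK parameters (maximum observed drug concentration", with Cmax taken over the first 5 hours after a dose, and adds "area under the plasma concentration-time curve computed up to 5 hours after dosing". Both parameters are specified as those of PEA. Note 1 to the table says "Participation in the PK component of the study is optional".

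The Rationale explains the link between drug and analyte: "ETX-018810 is a prodrug of palmitoylethanolamide (PEA), an endogenous bioactive lipid".

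The sampling description is under Overall Design, and two of its sentences are incomplete in the public text. One begins "Subjects will take their first dose of investigational product in the clinic on Day 1 (baseline" and stops after the closing bracket and a comma. The other reads "Blood specimens for plasma concentrations of PEA and for calculation of plasma pharmacokinetic (PK) parameters of PEA will be obtained before" and then ends. The Statistical Analysis Plan part of the Synopsis covers populations, weekly averages and the MMRM, and says nothing about PK. Treatment Groups and Duration gives 1:1 allocation to ETX-018810 or placebo. No visible text says whether placebo subjects are sampled for PK.

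**The concern.** The objective concerns the drug, but the measured analyte is a substance that the body also makes. Cmax is described as an observed maximum, and neither Cmax nor AUC0-5h is said to be adjusted for the level present before dosing. Taken at face value, each parameter is drug-derived PEA plus an endogenous offset.

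If such values were read as exposure from ETX-018810, they would be too high. Ratios of exposure between subjects with similar endogenous levels would also be pulled towards 1. A reader could then misjudge how much PEA the prodrug delivers and how variable that delivery is. The obvious remedy would be to subtract each subject's pre-dose value and report corrected parameters beside the observed ones.

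**Working it through.** **Inputs.** From the documents: the analyte (PEA, endogenous), the parameters (Cmax over 5 h and AUC0-5h) and the 5 h window. The documents give no endogenous level, no drug-derived level and no number of PK subjects, so there is no plan figure to reproduce. The figures below rest on assumed ranges.

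**Identity.** Assume a flat endogenous level C0 that adds to drug-derived PEA:
- observed AUC0-5h = drug-derived AUC0-5h + 5 h × C0
- observed Cmax = drug-derived Cmax + C0

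If f is the endogenous share of the observed value, the overstatement of the drug-derived value is f/(1 − f). For f = 1%, 5%, 10%, 25% and 50% this gives 1.0%, 5.3%, 11.1%, 33.3% and 100%.

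**Same calculation by exposure ratio.** Let r be mean drug-derived PEA over 0–5 h divided by C0. For AUC, the endogenous share is 1/(1 + r) and observed over drug-derived is (1 + r)/r. For Cmax, with an assumed drug-derived peak of twice its 0–5 h mean, put 2r in place of r. A true two-fold difference in drug-derived AUC between two subjects with the same C0 appears as (1 + 2r)/(1 + r).

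| r | Endogenous share of AUC | Observed / drug-derived AUC | Observed / drug-derived Cmax | Two-fold difference appears as |
|---|---|---|---|---|
| 0.25 | 80% | 5.0 | 3.0 | 1.20 |
| 1 | 50% | 2.0 | 1.5 | 1.50 |
| 5 | 17% | 1.2 | 1.1 | 1.83 |
| 10 | 9% | 1.1 | 1.05 | 1.91 |

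The direction follows from the identity. The size depends wholly on r, and nothing in the documents locates r within the table. The last column also needs equal endogenous levels; absolute differences are unchanged by a common offset.

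**What subtraction would cost.** If the pre-dose value is 30% above the 0–5 h endogenous mean, corrected AUC is too low by 0.30/r of drug-derived AUC: 30% at r = 1 and 3% at r = 10. The uncorrected value is too high by 1/r: 100% and 10%. Subtraction is closer to the truth whenever the pre-dose value lies between zero and twice the 0–5 h endogenous mean. That supports subtraction as sensible practice. It does not show that the plan omits it.

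**Is the omission established?** The places where a correction could be stated are these:
- Table S-1 is a synopsis table that names parameters in one line. Baseline rules are not normally given at that level.
- Overall Design stops mid-sentence in the PK sampling text. The last surviving word suggests a sample taken ahead of an event, most naturally the dose.
- The Synopsis statistical section gives no PK method, corrected or uncorrected.

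The visible text therefore leaves the handling unknown; it does not show that there is none.

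**The case for a change.** The best argument for acting is that the endpoint cell, unlike the sampling sentence, is complete and describes Cmax as observed. A pre-dose sample corrects nothing unless a rule says how to use it, and that rule would take one line of SAP text and one derived variable per parameter. Under plausible assumptions the gain is real. Take a between-subject CV of 40% for the endogenous level. The root-mean-square error for drug-derived mean concentration is then √(1 + 0.40²) = 1.08 endogenous units uncorrected. With a 30% CV of the pre-dose value around the 0–5 h mean, it is 0.30 × 1.08 = 0.32 corrected.

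Much of this stands. Uncorrected PEA should not be presented as exposure from the drug alone, and showing corrected values beside observed ones would be good reporting. Three things keep it from being a fault in the plan:
- The wording about an observed maximum is the ordinary expansion of Cmax, and the endpoint names PEA as the analyte. As a measure of PEA exposure it is right.
- Raw concentrations belong to the endpoint, so correction can be done at analysis if a pre-dose sample exists. The visible text states no PK hypothesis test that the choice could sway.
- Any fixed rule depends on withheld facts. The day of the profile is not visible. If it were at the end of Week 4, subtracting a Day 1 value would assume stability over four weeks rather than 5 hours.

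**Conclusion.** No change follows. The point is sound pharmacokinetics: observed PEA contains an endogenous part, and an analyst summarising these data should say whether values are corrected, which pre-dose value is subtracted, and whether placebo subjects provide a reference. But the concern rests on the absence of a statement in text that is cut off where the sampling is described, and in a synopsis with no PK analysis section. A missing rule is not shown.

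If no correction were made and the values were read as drug-derived, the overstatement of AUC0-5h would be 1% to 100% for an assumed endogenous share of 1% to 50%, and five-fold inflation at an assumed r of 0.25. These figures assume a flat, additive endogenous level, and the documents cannot say which applies, so materiality is unproven. Whatever the size, it is confined to an optional secondary component. The Week 4 pain comparison and its MMRM are unaffected. This is a gap in detail that a PK analyst can fill from the concentrations already planned, provided a pre-dose sample is among them.

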### Overall Design:

This is a prospective, Phase 2, multicenter, randomized, double-blind, placebo-controlled, parallel-group study to evaluate the efficacy, safety, and tolerability of ETX-018810 in male and female subjects aged  $\geq 18$  and  $\leq 75$  years with type 1 or 2 diabetes mellitus; diabetic neuropathy of a symmetrical nature in the lower extremities for  $\geq 6$  months to  $\leq 10$  years, with a score of  $\geq 3$  on the Michigan Neuropathy Screening Instrument (MNSI); and at least moderate pain intensity on the Patient Global Impression of Severity (PGI-S) scale. The study will include a screening period (maximum of 4 weeks), a 4-week treatment period, and a 1-week posttreatment follow-up period. Each subject will participate in the trial for up to approximately 9 weeks.

After providing written informed consent, potential study subjects will be screened for study eligibility during the maximum 4-week screening period. Subjects who meet the study entry criteria will be trained in the use of the electronic diary (eDiary) and in the completion of the Pain Intensity Numeric Rating Scale (PI-NRS), completion of the Daily Sleep Interference Scale (DSIS), and documentation of rescue medication use (acetaminophen) and will be instructed to discontinue any prohibited medications at the screening visit. Subjects will record their PI-NRS score over the last 24 hours once daily in the evening, their DSIS score once daily in the morning, and their rescue medication use once daily in the evening in the eDiary from screening

[figure not shown]
until the baseline/Day 1 visit. The values that are recorded for the PI-NRS and DSIS on the last 7 days before the baseline/Day 1 visit will be used to determine the baseline scores. Subjects whose average pain intensity over these 7 days meets the study-specified threshold, who completed the PI-NRS and DSIS in the eDiary on at least 5 of the 7 days before the baseline/Day 1 visit, and who continue to meet all other study eligibility criteria will be enrolled in the study. The baseline assessment of eligibility will be made using a computerized screening algorithm on the basis of the information that is recorded in the eDiary. The investigator, site team, and study monitors will be blinded to the screening algorithm. The investigator/site staff will be informed as to whether the algorithm classifies the subject as eligible or ineligible and will inform the subject if he/she is eligible to continue in the study. Subject will be randomized to receive double-blind treatment with ETX-018810 1000 mg or placebo twice daily (BID) for 4 weeks at the baseline/Day 1 visit.

Subjects will continue to use the eDiary to record their average pain intensity over the last 24 hours on the PI-NRS (once daily in the evening when they take their second daily dose of investigational product), their sleep interference as a result of the neuropathic pain on the DSIS (once daily in the morning when they take their first daily dose of investigational product), and rescue medication use (once daily in the evening when they take their second daily dose of investigational product) throughout the 4-week double-blind treatment period. Subjects will be allowed to take acetaminophen at a dose of up to 2600 mg/day for up to 3 consecutive days, but for no more than a total of 7 days, for non-DPNP-related pain (headache, toothache, etc) or for breakthrough pain due to DPNP.

Subjects will be contacted by telephone to review their status at the end of Week 2 and will report to the clinic for an end-of-treatment (EOT) visit at the end of Week 4. A final posttreatment follow-up telephone contact will be made 1 week after the last dose of investigational product (Week 5) to inquire about adverse events (AEs) and concomitant medication use. Subjects who discontinue from the study before completing the planned 4 weeks of treatment will undergo an early termination visit, which will include the evaluations that are scheduled for the Week 4 visit. If an ongoing automated review of the eDiary reveals that the subject is not complying with study procedures, site personnel will contact the subject to discuss any issues in an effort to improve compliance.

Subjects will take their first dose of investigational product in the clinic on Day 1 (baseline),  

Blood specimens for plasma concentrations of PEA and for calculation of plasma pharmacokinetic (PK) parameters of PEA will be obtained before 

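### The acetaminophen efficacy endpoint pools use for DPNP with use for other pain, and the diary as described records no reason that would separate them

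*Combined protocol and SAP*

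**What the plan says.** Under the secondary objective "To evaluate the efficacy of ETX-018810 on additional measures of pain and disability", Table S-1 lists the endpoint "Amount and pattern of acetaminophen use". Nothing in the table restricts it to acetaminophen taken for DPNP.

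Overall Design allows "acetaminophen at a dose of up to 2600 mg/day for up to 3 consecutive days, but for no more than a total of 7 days", and allows it "for non-DPNP-related pain (headache, toothache, etc) or for breakthrough pain due to DPNP". One allowance covers both reasons.

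On data capture, footnote 5 to Table S-1 reads: "Subjects will record rescue medication (acetaminophen) use in the eDiary once daily in the evening". Overall Design describes the entry in the same way for screening and for the treatment period. It calls all such use rescue medication, and no reason for use is mentioned anywhere. The Statistical Analysis Plan section of the synopsis gives no rule for dividing use by reason and no specific analysis of this endpoint; it says that continuous data are summarized descriptively.

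**The concern.** An efficacy endpoint in a DPNP trial should reflect DPNP. Here a subject who takes acetaminophen for toothache contributes to the endpoint exactly as one who takes it for breakthrough neuropathic pain. The plan expects both kinds of use, since it names headache and toothache as permitted reasons.

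Two readings of the result are then at risk. If the arms look similar, a real reduction in DPNP rescue may be hidden by unrelated use. If total use is lower on active, the data as described cannot show whether subjects needed less relief for DPNP or for something else. The Rationale section cites activity of PEA in inflammatory as well as neuropathic pain models, so one cannot simply assume that treatment leaves the other use untouched.

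**Working it through.** The plan states no expected acetaminophen use, so there is no figure of its own to reproduce. The check has three parts.

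**1. What the endpoint contains**

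| Element | Where | Limited to DPNP? |
|---|---|---|
| Objective served | Table S-1, secondary | Efficacy in this DPNP trial |
| Endpoint | Table S-1, secondary | No |
| Permitted reasons for use | Overall Design | No: DPNP or other pain |
| Diary entry | Table S-1 footnote 5; Overall Design | No reason mentioned |
| Analysis rule | Statistical Analysis Plan section | None given |

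Each row is silent or inclusive, so on the text supplied the endpoint is total acetaminophen use.

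**2. Effect on the comparison (all usage rates assumed)**

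Let P and A be mean DPNP rescue days on placebo and active, and u the mean unrelated days, equal in both arms and on different days from DPNP use.

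- Observed difference = (P + u) − (A + u) = P − A, whatever u is.
- Observed relative reduction = (P − A) / (P + u).
- Standard error of the difference, assuming Poisson day counts and the planned 81 per group = √[(P + A + 2u) / 81].

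With P = 2.0 and A = 1.4:

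| u | Means, placebo v active | Difference | Relative reduction | Standard error | Difference / SE |
|---|---|---|---|---|---|
| 0 | 2.0 v 1.4 | 0.6 | 0.6/2.0 = 30% | √(3.4/81) = 0.205 | 2.9 |
| 0.5 | 2.5 v 1.9 | 0.6 | 0.6/2.5 = 24% | √(4.4/81) = 0.233 | 2.6 |
| 1 | 3.0 v 2.4 | 0.6 | 0.6/3.0 = 20% | √(5.4/81) = 0.258 | 2.3 |
| 2 | 4.0 v 3.4 | 0.6 | 0.6/4.0 = 15% | √(7.4/81) = 0.302 | 2.0 |

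Balanced unrelated use leaves the mean difference alone, shrinks the percentage, and widens the standard error.

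**3. The shared limit**

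The allowance is 7 days in total; if it applies to the treatment period, that is 7/28 = 25% of days. Days spent on other pain then leave fewer for DPNP, so the mean difference can shrink too when use is heavy. Taking observed days as the smaller of 7 and a Poisson count:

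- At 2.0 v 1.4 days of DPNP need, the expected difference is 0.60 with no unrelated days and 0.55 with 2 per arm.
- At 4.0 v 2.8 days, it is 1.13 with none and 0.84 with 2 per arm; the relative reduction falls from 29% to 15%.

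So the statement that balanced use does not bias the difference holds well when use is light, and less well when the limit often binds.

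**The case against.** **Only a percentage shrinks.** In the main example the difference stays at 0.6 days, and the plan specifies neither a percentage-reduction estimand nor a test for this endpoint. That stands, and it is why the point concerns interpretability and noise rather than bias. It does not remove the problem that a DPNP efficacy measure includes use for other pain.

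**The documents are only a synopsis with a short analysis summary.** A fuller diary specification could hold a reason field, and concomitant medication is asked about at the follow-up call. Also fair: the finding is about the diary as described. But no analysis described here draws on a reason for use from any source.

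**Total use is objective and attributed use is not.** Asking subjects to name the reason brings in judgment after randomization. Acetaminophen taken for a headache may also affect that day's pain score, so total use matters for interpreting the PI-NRS. This stands in full: DPNP-related use should be reported beside total use, not in its place.

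**A stronger reading is tempting.** Overall Design asks subjects to "record their average pain intensity over the last 24 hours on the PI-NRS", while the same sentence ties the DSIS to "their sleep interference as a result of the neuropathic pain on the DSIS". A reader might infer that the PI-NRS takes in any pain, and that headache and toothache therefore dilute the primary endpoint and the 7-day eligibility average. The documents do not support that. The wording of the PI-NRS item and the content of the subject training are not in the text. Elsewhere the synopsis also mentions the DSIS without the neuropathic qualifier, so the contrast may be mere abbreviation. The primary objective is "To evaluate the efficacy of ETX-018810 on neuropathic pain via daily pain measurements", which points to a neuropathic anchor.

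**Conclusion.** The point holds for the acetaminophen endpoint. As described, it counts all permitted use, and the diary offers no way to isolate use for DPNP.

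Its size cannot be calculated from the documents. Under the assumed rates, a 30% reduction in DPNP rescue days appears as 24% to 15% with 0.5 to 2 unrelated days per subject. That rests on unrelated use being equal between arms, unaffected by treatment, and on separate days. Under those conditions, and with the 7-day limit seldom reached, the mean difference is not biased.

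This is a worthwhile, inexpensive improvement to one of several secondary efficacy endpoints. It is not evidence against the primary endpoint: the inference that non-DPNP pain dilutes the PI-NRS goes beyond the text, and what remains there is a request to confirm the item wording.

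**What to change.** - Add one item to the evening rescue entry: reason for acetaminophen (DPNP, other pain, or both).
- Report amount and days of acetaminophen taken for DPNP alongside amount and days of total use, and state in advance how entries marked as both are counted.
- Confirm that the PI-NRS item and the subject training ask about neuropathic pain, and quote the item in the plan.
- The analysis summary is written in the past tense. If data collection is already complete and no reason was recorded, label the endpoint as total acetaminophen use and do not interpret it as DPNP rescue.

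The cost is one diary question, a line of training and an endpoint definition. The downside is a few seconds of burden on rescue days and some misattribution by subjects, which the total-use summary guards against. The rescue allowance itself is not changed.
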